	
 - Assess changes in tumor size on radiographic images with neoadjuvant endocrine therapy and correlate with changes in biomarkers and Ki-67.
Endpoints	
Primary endpoints are:
 
 - Change in cancer cell protein levels of HER family members (HER1-4) with neoadjuvant endocrine therapy and association with Ki-67. We hypothesize that the expression of one or more HER proteins (HER1-4) will be upregulated in at least 50% of tumors after four weeks of neoadjuvant endocrine therapy and this upregulation will correlate with Ki-67 expressed in more than 10% of cancer cells. 
Secondary end points are:
 
 - Determine whether an increased proportion of therapy-resistant CK5+ progenitor cells are negatively correlated with Ki-67 response and tumor volume reduction, in response to neoadjuvant endocrine therapy. - Assess changes in the % expression of ER and PR in pre- and post-treatment breast cancer tumor specimens and their correlations with Ki-67 and radiographic responses. - Assess changes in BTK protein expression with neoadjuvant endocrine therapy and correlation with responses. - Changes in iron-related protein expression, i.e., transferrin, ferritin, ferroportin and ribonucleotide reductase with neoadjuvant endocrine therapy and correlation with responses. - Changes in PD-L1 and PD-L2 protein expression with neoadjuvant endocrine therapy and correlation with responses. - Assess changes in tumor size on radiographic images with neoadjuvant endocrine therapy and correlate with changes in biomarkers and Ki-67. 
Chart review planned at about five years from completion of study to assess patient outcomes, i.e., ipsilateral, contralateral or distant recurrences.

Study Design	Exploratory study.
Study Agent/ Intervention Description	This is an exploratory interventional study that initiates standard-of-care anti-estrogen treatment preoperatively for four weeks, +/- 1 week.
Number of Subjects	37
Subject Participation Duration	Patients to be treated C1D1 for four weeks +/- 1 week.

Duration of Follow up	Within 30 days after completion of study treatment
Long term Follow up	As standard of care, patients will be followed by oncology provider(s) at least annually from surgery (+/- 3 months). Cancer outcomes up to five years post-treatment will be collected by chart review.
Estimated Time to Complete Enrollment:	2 years

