5. Questions regarding OnCore systems and data reporting should be reported to OnCore® data management.
6. Questions regarding patient eligibility and registration procedures should be directed to the principal investigator, [name], MS ([contact], [contact], office [contact]).
7. Subject Withdrawal. Given the short nature of the treatment regimen (three to five weeks), and none or few low-grade toxicities are expected, it is not considered likely that a large percentage of patients will withdraw from the study, once endocrine treatment has begun. However, subjects have the right to withdraw from the study at any time. In the rare case that a patient withdraws from the protocol after the initiation of treatment, only the data collected up until the date of withdrawal will be used in analysis.
8. A subject may be withdrawn from the study, if she wishes to decline treatment on the study. Subjects may also be withdrawn if there is a violation of the protocol inclusion and exclusion criteria, as deemed relevant by the treating physician and the principal investigator. As these patients would be withdrawn prior to delivery of study-related treatment, they will then be replaced on the study and not counted toward the total accrual goal of 39 patients. Similarly, patients withdrawing for any other reason prior to delivery of treatment will be replaced on the study and not counted toward the total accrual goal.
9. Patients who withdraw from the study should be treated in accordance with normal standard of care. Follow-up will be per the discretion of the patient's treating physicians, but at a minimum be in accordance with NCCN guidelines.

Pretreatment Period

Screening Assessments

Once the informed consent is signed, proceed with the screening procedures and assessments which must be completed within 28 days of prior to enrollment.

- Physical examination
- Vital signs
- Complete medical history
- Performance status (ECOG, KPS, etc.) (Appendix.2)

- Adverse event assessment
- Current medications
- Blood chemistry assessment, including
 - Complete blood count (CBC) with differential and platelet count
 - Alkaline phosphatase, aspartate aminotransferase/alanine aminotransferase - (ALT/AST)
 - total bilirubin
 - calcium
 - phosphorus,
 - creatinine,
 - potassium,
 - sodium,
 - chloride,
 - bicarbonate,
 - fasting lipid panel (low-density lipoprotein [LDL], total cholesterol, triglycerides) - within the past 12 months.

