5. Other less commonly reported side effects are anti-estrogen symptoms, i.e., hot flashes, mood changes and weight changes. Some of the rare but serious side effects, such as ischemic cardiovascular event, thromboembolic event or uterine cancer with tamoxifen are long-term side effects and are not expected to occur during this short course of neoadjuvant treatment. Similarly, decrease in bone density with aromatase inhibitors is a slow and long-term side effect, not expected to be seen during the four-week study period.
6. There are no dose modifications or reductions recommended with endocrine treatment.

VII. STATISTICAL CONSIDERATIONS

Statistical analyses:

Demographic and baseline characteristics, such as age, race, weight, values of all biomarkers pre and post-treatment, response measures will be summarized, using means, standard deviations, medians, ranges for continuous variables, and proportions for categorical variables.

This is an exploratory study to gather information on how frequently protein levels of HER growth factor receptors (HER1-4) are upregulated along with changes in other study biomarkers and correlation with Ki-67 in response to short-term neoadjuvant endocrine in early stage HR+ breast cancer. We hypothesize that expression of one or more HER proteins (HER1-4) will be upregulated in at least 50% of tumors after four weeks of neoadjuvant endocrine therapy and this upregulation will correlate with Ki-67 expressed in more than 10% of cancer cells, as compared to upregulation in 30% or less of tumors without the therapy. The change in Ki-67 expression will be dichotomized, as a categorical variable with $\geq 10\%$ increase coded as high and $< 10\%$ coded as low.

- a) For the primary outcome: An exact binomial one sample test of proportions will be used for to test the hypothesis that proportion of upregulated HER proteins will be at least 50% after therapy versus the null hypothesis that the proportion of upregulated HER proteins is not greater than 30%.
- b) For analyzing - the differences in proportion of upregulated HER proteins between the high difference in Ki-67 and low difference in Ki-67 groups, two sample tests of proportions will be used.

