- c) Similarly, appropriate two sample tests will be used to test differences in biomarkers between the high difference in Ki-67 and low difference in Ki-67 groups. We will use the appropriate kind of regression instead of two sample tests, to test differences in biomarkers between the high difference in Ki-67 and low

difference in Ki-67 groups if we need to adjust for covariates.

- d) Additionally, regression analysis will also be done to evaluate the changes in the biomarkers and their association with patient specific covariates, such as age, race and other relevant predictors of interest.

Radiographic responses will be assessed by WHO criteria. Radiographic response rates will be measured as the rate of complete response (CR) or partial response (PR) in patients treated with neoadjuvant endocrine therapy. Complete response is defined as the resolution of tumor on post-treatment imaging as compared with pretreatment imaging, while partial response is defined as 50% reduction in tumor size on post-treatment imaging, as compared with pretreatment imaging. We will estimate the rates of response with 95% confidence intervals. We will use logistic regression (and other generalized linear models as appropriate) to measure association between the response rates and patient specific covariates such as age, race and other relevant predictors of interest.

We will use a family type I error rate of 0.05 significance throughout with Bonferroni adjustments for multiple testing wherever appropriate, so that the overall family type I error rate is maintained.

Sample Size and Power Calculation

To achieve at least 80% power at significance level of 0.05, when testing the one sided one sample hypothesis that the proportion of tumors with HER protein upregulation with neoadjuvant endocrine therapy is at least 50% versus the null hypothesis that the proportion is no larger than 30%, **the minimum number of patients required is 37.**

Early Stopping for Futility

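### The 0.05 family error rate has no defined family: N = 37 allows nothing for multiplicity, and the sections disagree on whether the Ki-67 association is a second primary test

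*Combined protocol and SAP*

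**What the plan says.** **Error rate.** Section VII, Statistical analyses, closes with: "We will use a family type I error rate of 0.05 significance throughout with Bonferroni adjustments for multiple testing wherever appropriate". No list of tests follows, and the section does not say whether the primary binomial test is in the family.

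**Sample size.** Section VII, Sample Size and Power Calculation, reads: "To achieve at least 80% power at significance level of 0.05, when testing the one sided one sample hypothesis". The hypotheses are a HER upregulation proportion of at most 30% against at least 50%, and "the minimum number of patients required is 37". No other test enters the calculation.

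**Where the Ki-67 association is primary.** The Protocol Summary lists under its primary endpoints: "Change in cancer cell protein levels of HER family members (HER1-4) with neoadjuvant endocrine therapy and association with Ki-67". The Primary Objectives entry in the Summary, the Primary Objective in Section II and the Primary End point in Section IV also include it.

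**Where it is not.** Section VII item a is introduced as the single primary analysis: "For the primary outcome: An exact binomial one sample test of proportions will be used for to test the hypothesis". Item b, the two-sample comparison of upregulation between the Ki-67 groups, does not carry that label and has no alpha, sidedness, effect size or power. Early Stopping for Futility restates the primary objective as HER upregulation, without Ki-67.

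**The concern.** A family-wise promise can be carried out only if the family is known. Here the number of primary tests is one or two depending on the section read, and Bonferroni applies only where it is judged appropriate. Two analysts following this text could use different rejection thresholds for the same data.

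The contested result is exactly 17 upregulated tumors of 37. It is significant if item a has the full 0.05 and not significant if item a has 0.025. The data are meant to inform a randomized trial of endocrine plus anti-HER therapy, so the plan should fix in advance whether that result counts as positive.

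**Working it through.** **Inputs.** From Section VII: p0 = 0.30, p1 = 0.50, one-sided alpha 0.05, target power 80%, n = 37, exact binomial test. Assumption, because the documents give no family: two primary tests (items a and b), with an equal split where Bonferroni is applied.

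**1. Reproduce the stated N.** Arcsine formula: n = ((z₀.₉₅ + z₀.₈₀)/h)², with h = 2·asin(√0.5) − 2·asin(√0.3) = 1.5708 − 1.1593 = 0.4115.
n = ((1.6449 + 0.8416)/0.4115)² = 36.5, rounded up to 37. The stated figure is reproduced with the whole one-sided 0.05 given to item a, so it contains no multiplicity allowance.

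**2. Exact test at n = 37.** Take the smallest r with P(X ≥ r | 37, 0.30) ≤ alpha. Power is P(X ≥ r | 37, 0.50).

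| Alpha for item a | Reject at | Attained size | Power at 50% |
|---|---|---|---|
| 0.05 (no split) | 17 or more | 0.0295 | 74.4% |
| 0.025 (equal split, two tests) | 18 or more | 0.0131 | 62.9% |

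The multiplicity effect is the difference between the rows: 74.4 − 62.9 = 11.5 points, up to rounding. The gap from 80% to 74.4% exists before any adjustment.

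**3. N under an equal split.** Arcsine: ((1.9600 + 0.8416)/0.4115)² = 46.3, so 47. The exact test first reaches 80% at n = 47 (80.9%) and stays at or above 80% from n = 54.

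**4. Family rate with no split, if either test can succeed.**
- Nominal bound: 0.05 + 0.05 = 0.10 (1 − 0.95² = 0.0975 if independent).
- With the attained size of item a at n = 37: 0.0295 + 0.05 = 0.0795, about 0.08. This takes the size of item b to be at most 0.05.

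**5. Readings that keep the threshold at 17.**
- Item a is the only primary test: 0.05 is spent once.
- Both parts must succeed: each can be tested at 0.05 without a split.
- Fixed sequence, a then b: if the item a null is true, any false claim requires item a to reject (at most 0.0295). If it is false, the only possible false claim is item b (at most 0.05).
- Unequal Bonferroni: 0.0295 for item a and 0.05 − 0.0295 = 0.0205 for item b.

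**6. How robust is the unequal split?** It relies on the discreteness of the test at n = 37. Section V gives an accrual goal of 39 ("not counted toward the total accrual goal of 39 patients"). At n = 39 the threshold is still 17 but the attained size is 0.04998, which leaves 0.05 − 0.04998 = 0.00002 for item b. The fixed sequence does not depend on n in this way.

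**The case against.** The strongest reply is that nothing is broken. Section VII labels one test as primary, the futility text agrees, and one primary test at 0.05 needs no adjustment. Even with two parts, the hypothesis joins them with a conjunction, and a claim that requires both needs no split. The study calls itself exploratory, accepts that significance may not be reached, and says HER findings will not affect safety or clinical management.

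Much of this stands. A reader might infer that the 0.05 family rate and the stated power are incompatible. The documents do not support that, because each reading in step 5 holds the family rate without moving the item a threshold. Nor does the plan promise Bonferroni everywhere: in the quoted sentence it is the 0.05 family rate that applies to all tests, while Bonferroni is conditional.

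A reader might also divide alpha by four for HER1-4 (19 or more, power 50.0%) or over some 13 tests (20 or more, power 37.1%). These cases have little basis in the text. The primary outcome is one composite per tumor, any of the four proteins upregulated, and the plan nowhere puts the primary test in one family with the secondary markers. That the choice would be made after seeing the data is likewise an inference; the plan only leaves it unstated.

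What the reply does not answer is that four statements of the primary objective or endpoint include the Ki-67 association, and the plan adopts none of the rescuing readings. The exploratory label reduces the consequence. It does not supply the missing rule, since the sponsor chose a formal hypothesis, a power target and family-wise control.

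**Conclusion.** The point holds as a gap in specification with a measurable effect. The family is undefined, N = 37 has no multiplicity allowance, and the documents disagree on whether item b is primary. Under an equal two-way Bonferroni split, the threshold moves from 17 to 18 of 37 and exact power from 74.4% to 62.9%. With both tests at 0.05 and either sufficient, the family rate could reach about 0.08 at n = 37. Both figures are conditional on item b being a second primary test; if item a is the only one, neither applies.

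It would be wrong to attribute the whole gap between 80% and 62.9% to multiplicity. The planned exact test has 74.4% power at an unsplit 0.05, which is a separate sizing defect.

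This should be settled before analysis. It does not undermine the design.

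**What to change.** 1. Make the primary objective and endpoint consistent across the Protocol Summary and Sections II, IV and VII, and say whether item b is a primary test.
2. Replace Bonferroni for the primary family with a fixed sequence: item a at one-sided 0.05, then item b at 0.05 only if item a rejects. State the sidedness of item b. This holds the primary family at 0.05 with no split, no extra patients for multiplicity, and the item a threshold unchanged.
3. Put the secondary markers in a separate family labelled exploratory, list its tests, and use Holm in place of Bonferroni. Holm controls the same error rate and is never less powerful. State that 0.05 applies to each family; across both, the bound is 0.05 + 0.05 = 0.10.

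**Cost.** Changes to protocol and SAP wording only. The disclosed downside is that item b cannot be claimed unless item a succeeds. At n = 37 and a true rate of 50%, that caps the chance of claiming item b at 74.4%. If the sponsor wants item b claimable alone, alpha must be shared. An equal split would need at least 47 patients for 80% exact power on item a.

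The fix leaves the 74.4% as it is. That figure, and the difference between 37 and the accrual goal of 39, must be dealt with separately.

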Statistical Methodology:	
We hypothesize that expression of one or more HER proteins (HER1-4) will be upregulated in at least 50% of tumors after four weeks of neoadjuvant endocrine therapy and this upregulation will correlate with Ki-67 expressed in more than 10% of cancer cells, as compared to upregulation in 30% or less of tumors without the therapy. The change in Ki-67 expression will be dichotomized, as a categorical variable with $\geq 10\%$ increase coded as high and $< 10\%$ coded as low.
 
 - For the primary outcome: An exact binomial one sample test of proportions will be used for to test the hypothesis that proportion of upregulated HER proteins will be at least 50% after therapy versus the null hypothesis that the proportion of upregulated HER proteins is not greater than 30%. - For analyzing - the differences in proportion of upregulated HER proteins between the high difference in Ki-67 and low difference in Ki-67 groups, two sample tests of proportions will be used. - Similarly, appropriate two sample tests will be used to test differences in biomarkers between the high difference in Ki-67 and low difference in Ki-67 groups. We will use the appropriate kind of regression instead of two sample tests, to test differences in biomarkers between the high difference in Ki-67 and low difference in Ki-67 groups if we need to adjust for covariates. - Additionally, regression analysis will also be done to evaluate the changes in the biomarkers and their association with patient specific covariates, such as age, race and other relevant predictors of interest. 
Radiographic responses will be assessed by WHO criteria. We will use logistic regression (and other generalized linear models as appropriate) to measure association between the response rates and patient specific covariates such as age, race and other relevant predictors of interest.

	
To achieve at least 80% power at significance level of 0.05, when testing the one sided one sample hypothesis that the proportion of tumors with HER protein upregulation with neoadjuvant endocrine therapy is at least 50% versus the null hypothesis that the proportion is no larger than 30%, the minimum number of patients required is 37.

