3. Purely noninvasive breast cancer (i.e., ductal carcinoma *in situ*, lobular carcinoma *in situ*).
4. Men with breast cancer. Male breast cancer is a rare event and it is unclear if neoadjuvant endocrine treatment approach is safe in men.
5. Medical, psychiatric or other condition that would prevent the patient from receiving the protocol therapy or providing informed consent.
6. Pregnant or lactating women are ineligible.

IV. STUDY DESIGN AND TREATMENT PLAN

General description: This is an exploratory interventional study to investigate changes in HER-protein expression along with other biomarkers of interest and correlations with tumor cell proliferation and responses in patients with HR+ HER2 negative early stage breast cancer treated with neoadjuvant endocrine therapy.

Number of subjects: 37

Primary End point: Determine the frequency of increased protein expression of **HER family of receptor tyrosine kinases** in tumors, following treatment with neoadjuvant endocrine therapy and their correlation with Ki-67 tumor responses.

Secondary End points:

- To determine changes in additional selected molecular markers (CK5+/ER-progenitor cells, PD-L1, PD-L2, BTK, iron-related proteins) and correlate with Ki-

67 responsiveness to endocrine therapy in our pre- and post-treatment tumor specimens.

- Assess changes in tumor size on radiographic images with neoadjuvant endocrine therapy and correlate with changes in biomarkers and Ki-67.

Study Timeline:

Primary completion: We expect that the study will reach primary completion 24 months from the time the study opens to accrual.

Study completion: We expect that the study will reach study completion 36 months from the time the study opens to accrual.

Treatment Plan

1. At MCW, all patients undergo diagnostic mammogram and ultrasound of the breast (standard of care) to further evaluate an abnormal breast finding and to obtain core biopsies for diagnostic purposes. If the tumor is visualized on both imaging modalities, at least the largest bidimensional measurements will be recorded. If possible, three-dimensional measurements of tumors will be obtained.
2. Patients with a diagnosis of ER and/or PR positive, HER2 negative node negative invasive breast cancer would be screened for this study (refer to the schema).
3. Node negativity will be established by clinical exam and/or ultrasound

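### With 37 patients the planned exact binomial test has 74% power, not the stated 80% or more, and the protocol also gives an accrual goal of 39

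*Combined protocol and SAP*

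**What the plan says.** Section VII, Statistical analyses, item a), and the Statistical Methodology entry of the Protocol Summary name the primary test: "An exact binomial one sample test of proportions will be used for to test the hypothesis". The sample-size paragraph, which appears in both places, sets the design:

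- **Target:** "To achieve at least 80% power at significance level of 0.05, when testing the one sided one sample hypothesis".
- **Alternative:** "the proportion of tumors with HER protein upregulation with neoadjuvant endocrine therapy is at least 50" percent.
- **Null:** "versus the null hypothesis that the proportion is no larger than 30" percent.
- **Result:** "the minimum number of patients required is 37".

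Section IV repeats "Number of subjects: 37", and the Protocol Summary also lists 37 subjects. Section V, Registration and Monitoring of Patients, item 8, says that patients withdrawn before treatment will be "replaced on the study and not counted toward the total accrual goal of 39 patients". Nothing explains the difference between 37 and 39. The sample-size paragraph names no formula and makes no allowance for patients without usable paired tissue.

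**The concern.** This is the only power statement in the plan, and it refers to the only test for which a sample size is justified. An exact binomial test can reject only at whole-number counts, so its real size and power move in steps. A sample size from a smooth approximation can then miss its target. If 37 came from such an approximation, readers would believe that a true 50% rate is missed at most one time in five when the actual risk is higher.

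Two accrual totals add to the problem. Site staff cannot tell when enrolment ends, and the analyst cannot fix the rejection count, which depends on n.

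A related point is how a positive result will be read. The hypothesis is worded as a rate of 50% or more, but the test is against 30%. Section VII plans 95% confidence intervals for the radiographic response rates and none for the HER upregulation proportion. A result that only just rejects could therefore be reported as support for 50%.

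**Working it through.** **Inputs, all from Section VII:** null p0 = 0.30, alternative p1 = 0.50, one-sided α = 0.05, target power 0.80, exact binomial test, n = 37. No outside assumption is needed.

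**1. Reproducing 37.** The arcsine formula for one proportion is n = ((z₀.₉₅ + z₀.₈₀)/h)², with h = 2·asin√p1 − 2·asin√p0.

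- h = 1.5708 − 1.1593 = 0.4115
- z₀.₉₅ + z₀.₈₀ = 2.4865
- n = (2.4865/0.4115)² = 36.5, rounded up to 37

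Other one-sided approximations give different numbers: 34.5 (→ 35) with null and alternative variances, 38.6 (→ 39) with the alternative variance only, and 39.3 (→ 40) with continuity correction. The plan states no formula, so the arcsine origin of 37 is an inference from the match.

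**2. The planned exact test at n = 37.** Take the smallest r with P(X ≥ r | n, 0.30) ≤ 0.05. Power is then P(X ≥ r | n, 0.50).

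| Reject at | Size at 30% | Power at 50% |
|---|---|---|
| ≥ 16/37 | 0.0604 (above 0.05) | 0.838 |
| ≥ 17/37 | 0.0295 | 0.744 |

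Only the second row is a valid 0.05-level test. Its type II error is 1 − 0.744 = 0.256. The uncorrected z-test and the mid-p test both reject at 16/37. They reach 83.8% power only by accepting a true one-sided size of 6.0%.

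**3. Neighbouring sample sizes, exact test.**

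| n | Reject at | Size | Power |
|---|---|---|---|
| 35 | ≥ 16 | 0.036 | 0.750 |
| 36 | ≥ 16 | 0.047 | 0.797 |
| 37 | ≥ 17 | 0.029 | 0.744 |
| 38 | ≥ 17 | 0.039 | 0.791 |
| 39 | ≥ 17 | 0.04998 | 0.832 |
| 40 | ≥ 18 | 0.032 | 0.785 |
| 41 | ≥ 18 | 0.041 | 0.826 |
| 42 | ≥ 19 | 0.026 | 0.780 |

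The smallest n with valid size and at least 80% power is 39. Power stays at or above 80% for every n only from 43 onward.

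**4. What rejection shows.** The boundary result is 17/37 = 46%, which is below 50%. Its exact (Clopper–Pearson) two-sided 95% interval is 29% to 63%, and the one-sided 95% lower bound is 31.8%. If the true rate were 45%, the test at 37 would still reject with probability 0.52. Rejection therefore supports a rate above 30% and says little about whether it reaches 50%.

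**The case against.** The strongest reply is that the study is exploratory. Sections I and VII both warn that statistical significance may not be reached, and Section VII says HER upregulation will not affect patient management. The exact test at 37 is conservative (size 0.029), so false positives are controlled, and the shortfall is about 6 points of power, or two patients. All of this is true, and it limits the harm. It does not make the power figure right: a general caution about significance does not tell the reader that power is 74%, and the plan itself chose a formal test, level, power and minimum n.

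Three narrower objections stand in part:

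- The documents do not say where 39 came from. It may be the exact-test minimum, an allowance for losses, or a leftover number. The contradiction with 37 remains whichever it is.
- 39 is a fragile choice. Section IV, Treatment Plan, item 10 admits patients with tissue for only some biomarkers, item 18 requires at least two weeks of treatment to be evaluable, and Section VII drops missing samples. With 38 evaluable patients power is 79.1%, again below target.
- The two-sided 95% interval at 17/37 includes 30% although the one-sided test rejects. This is normal when a two-sided interval accompanies a one-sided test, but the report should explain it or add the one-sided lower bound.

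The plan does state the null as 30%, so misreading a rejection as proof of 50% is a risk rather than a certainty. That point is secondary to the power error.

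**Conclusion.** The concern holds. For the test the plan names, 37 evaluable patients give 74.4% power at one-sided 0.05, which is 5.6 points below the stated minimum, with a type II error of about 26%. The figure 37 is not the minimum for 80% power under that test; 39 is, with power 83.2% provided all 39 are evaluable. Separately, current protocol text gives both 37 and 39 as the total. The power result rests only on the plan's own inputs. The explanation of how 37 arose, and any link between 39 and the exact test, are inferences and the conclusion does not depend on them. This must be corrected, because it is the plan's only power claim for its primary test.

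**What to change.** Choose one total and use it in the Protocol Summary, Section IV, Section V item 8 and Section VII.

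- **If 37 is kept:** state that with 37 evaluable patients the exact test rejects at 17 or more, with one-sided size 0.029 and power 74% at a true rate of 50%. Correct the 39 in Section V.
- **If 39 is intended:** replace 37 everywhere and state rejection at 17 or more of 39, size 0.04998 and power 83%. Say that these figures need 39 evaluable patients and that power is 79% at 38. Either add an allowance for unevaluable pairs or acknowledge the loss.

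In both cases, say that the rejection count will be recalculated for the evaluable number actually obtained, using the same exact rule. State that rejection supports a rate above 30%. Plan an exact 95% confidence interval for the HER upregulation proportion, with the one-sided lower bound if consistency with the test is wanted.

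The cost is protocol and SAP wording. Keeping 37 needs no extra patients but shows a less favourable power; moving to 39 adds two patients to the 37 and matches a number already in the protocol. An allowance for unevaluable pairs would add more.
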